7.7.1.3 Reporting Periods for Adverse Events and Serious Adverse Events

The safety reporting period for all AEs and SAEs is from start of dosing of any study drug on Cycle 1 Day 1 to 30 days after last dose of study drug (ZW25, palbociclib, and/or fulvestrant). However, all study protocol-related AEs are to be recorded from the time of informed consent. All SAEs that occur after the safety reporting period and are considered study treatment-related in the opinion of the investigator should also be reported to the sponsor.

SAEs will be followed until significant changes return to baseline, the event stabilizes (recovering/resolving) or is no longer considered clinically significant by the investigator, or the subject dies or withdraws consent. All non-serious AEs will be followed through the safety reporting period. Certain non-serious AEs of interest may be followed until resolution or return to baseline.

Potential Hy's Law cases ([Appendix F](#)) should be reported as SAEs (even before all other possible causes of liver injury have been excluded).

7.7.1.4 Serious Adverse Events Require Immediate Reporting

Within 24 hours of observing or learning of an SAE, investigators are to report the event to the sponsor, regardless of the relationship of the event to the study treatment regimen.

For initial SAE reports, available case details are to be recorded on an SAE form. At a minimum, the following should be included:

- Subject number
- Date of event onset
- Description of the event
- Study treatment, if known

The completed SAE form is to be emailed to the sponsor's representative within 24 hours (see email specified on the SAE report form).

Relevant follow-up information is to be submitted to the sponsor as soon as it becomes available.

7.7.1.5 Sponsor Safety Reporting to Regulatory Authorities

Investigators are required to report all SAEs, including anticipated SAEs, to the sponsor (see [Section 7.7.1.4](#)).

The sponsor will report all SAEs to regulatory authorities as required per local regulatory reporting requirements.

7.7.2 Adverse Events of Special Interest

Adverse events of special interest include absolute decreases in LVEF ≥ 10 percentage points from baseline, symptomatic heart failure, infusion-related reactions, and all \geq Grade 2 events of pneumonitis and/or interstitial lung disease, including pulmonary fibrosis.

Adverse events of special interest should be recorded as AEs and reported as SAEs when appropriate. When an event does not meet the criteria for an SAE, a form for AESIs should be

completed and submitted to the sponsor or sponsor safety representative. AESIs should continue to be followed until resolution or return to baseline.

7.7.3 Clinical Laboratory Tests

Samples for clinical laboratory tests will be obtained at selected time points specified in the assessment schedule ([Appendix A](#))

Clinical laboratory analyses may be performed at local laboratories. Any abnormalities in any of the laboratory parameters will be judged in relation to the reference ranges from the laboratory and to the clinical relevance assessed by the investigator.

The following parameters will be determined: hemoglobin, hematocrit, white blood cell count (total and differential), RBC count, platelet count, mean corpuscular volume, mean corpuscular hemoglobin (MCH), and MCH concentration. Coagulation parameters such as PT, INR, and PTT/ aPTT will also be required at specified time points; also, additional coagulation tests may be done per institutional standards for subjects taking fulvestrant.

The following parameters will be measured: creatinine, urea (or blood urea nitrogen [BUN]), AST, ALT, ALP, lactate dehydrogenase, total bilirubin, albumin, total protein, sodium, potassium, chloride, glucose, uric acid, calcium, magnesium, and phosphorus.

Urine will be screened for pH, glucose, ketones, blood, protein, and microscopy (if indicated).

For female subjects of childbearing potential, screening for pregnancy will be performed at screening and at predetermined time points during the study. These tests will be done using the blood samples taken for clinical chemistry. A urine pregnancy test is also acceptable.

7.7.4 Vital Signs

Vital signs measures include heart rate, blood pressure, respiratory rate, and temperature. Vital signs will be recorded at selected time points specified in the assessment schedule ([Appendix A](#)) and done in a standardized manner (i.e., after the subject has rested in the sitting position for 5 minutes). Postdose assessments should be done within approximately 30 minutes of the end of the ZW25 infusion.

7.7.5 Physical Examination

Physical examinations should include assessments of the following body parts/systems: abdomen, extremities, head, heart, lungs, neck, and neurological. Height will be measured only at screening. Weight will be measured as part of all physical examinations.

7.7.6 ECOG Performance Status

ECOG PS will be assessed at selected time points specified in the assessment schedule ([Appendix A](#)). The ECOG PS scores are described in [Appendix E](#).

7.7.7 Electrocardiogram

The 12-lead ECGs will be recorded at selected time points specified in the assessment schedule ([Appendix A](#)). The ECG will be recorded after at least a 10-minute rest. The date and an overall

interpretation of the ECG will be recorded in the CRF. The interpretation of the ECG will be assessed as normal or abnormal, and if abnormal as clinically significant or not. If the ECG is considered abnormal and clinically significant, the abnormality must be recorded in the CRF. At least the following parameters should be assessed: heart rate, PR interval, QRS complex, and QTcF.

7.7.8 Echocardiogram/MUGA

Echocardiograms or MUGAs are recorded at selected time points specified in the assessment schedule ([Appendix A](#)). Echocardiograms or MUGAs will be recorded locally and will be assessed for an estimate of the ejection fraction. The same method must be used throughout the study. Management of left ventricular dysfunction is described in [Section 5.2.3.1](#)

7.8 Appropriateness of Measurements

The efficacy planned for this study are widely used and generally recognized as reliable, accurate, and relevant to the disease condition.

The safety measures that will be used in this trial are considered standard procedures for evaluating the potential adverse effects of study medications.

Pharmacokinetic assessments are also common in clinical studies to help characterize dose-exposure-response relationships.

Immunogenicity is commonly assessed for biologics; therefore, standard tests will be performed to detect the possible presence of specific antibodies to ZW25.

8 DATA QUALITY CONTROL AND QUALITY ASSURANCE

8.1 Audit and Inspection

Study centers and study documentation may be subject to Quality Assurance audits during the course of the study by the sponsor or its nominated representative. In addition, inspections may be conducted by regulatory authorities or the Institutional Review Board (IRB) / Independent Ethics Committee (IEC) at their discretion.

The investigator must permit the IRB/IEC, the sponsor's auditors, and representatives from regulatory authorities to have direct access to all study-related documents and pertinent hospital or medical records for confirmation of data contained within the CRFs. Subject confidentiality will be protected at all times.

8.2 Monitoring

Data for each subject will be recorded on a CRF. Data collection must be completed for each subject who signs an ICF and undergoes any screening assessment.

In accordance with GCP and ICH guidelines, the study monitor will carry out source document verification at regular intervals to ensure that the data collected in the CRF are accurate and reliable. The frequency of monitoring visits will be as described in the Monitoring Plan but may be modified by the rate of subject recruitment.

A clinical monitoring plan will detail the tasks to be completed at each monitoring visit. This will at least include the following:

- Site monitoring procedures including review of the ICF, source document review, source data verification, and review of CRF data
- AE and SAE reporting
- Investigational product receipt, ordering, preparation and administration, storage, documentation, accountability, dosing compliance, and return/destruction

The monitoring visits also provide the sponsor with the opportunity to ensure the investigator's obligations and all applicable ICH or health authority regulation requirements are being fulfilled.

The investigator must permit the monitor direct access to all study-related documents and pertinent hospital or medical records for confirmation of data contained within the CRFs. Subject confidentiality will be protected at all times.

8.3 Data Management and Coding

Study centers will enter data directly into an electronic data capture system by completing the CRF via a secure internet connection. Data entered into the eCRF must be verifiable against source documents at the study center. Data to be recorded directly on the eCRF will be identified. Any changes to the data entered into the electronic data capture system will be recorded in the audit trail and will be FDA 21 CFR Part 11⁵ compliant and/or other region-specific electronic records regulatory requirements.

Medical coding will use Medical Dictionary for Regulatory Activities (MedDRA) for concomitant diseases and AEs and WHO Drug Dictionary for medications.

Missing or inconsistent data will be queried in the electronic data base to the investigator for clarification. Subsequent modifications to the database will be documented.

8.4 Drug Accountability

Each site will verify their inventory of study drug supplies throughout the study, and that study drug is received intact and in the correct amounts. The monitor may check the study supplies at each study center at any time during the study.

The study monitor will ensure that the site has correctly documented the amount of the study drug received, dispensed, and returned on the dispensing log. A full drug accountability log will be maintained at the study center at all times. All discrepancies must be accounted for and documented.

9 DATA ANALYSIS METHODS

9.1 Determination of Sample Size

No formal sample size calculations were performed for Part 1 of the study. Approximately 6 evaluable subjects will be enrolled in each dose cohort in Part 1 with up to six ZW25 and

⁵ FDA 21CFR11: Electronic Records; Electronic Signatures. April 2019. Available from: <https://www.accessdata.fda.gov/scripts/cdrh/cfdocs/cfcfr/CFRSearch.cfm?CFRPart=11>.

palbociclib dose level combinations evaluated; therefore, the approximate minimum and maximum sample sizes for Part 1 are 6 and 36 evaluable subjects, respectively.

Details regarding sample size for Part 1 and Part 2 of the study are presented in [Table 9](#).

Table 9: Sample Size Determination (Parts 1 and 2)

Study Part	Cohort or Stage	ZW25 Dose (mg/kg)	Palbociclib Dose (mg)	Sample Size ^b
1	1A	20	125	6
	1B	20	100	6 (if palbociclib de-escalation from cohort 1A recommended)
	1C	20	75	6 (if palbociclib de-escalation from cohort 1B recommended)
	1D	15	125	6 (if ZW25 de-escalation from cohort 1A recommended)
	1E	15	100	6 (if ZW25 de-escalation from cohort 1B or both ZW25 and palbociclib de-escalation from cohort 1A recommended)
	1F	15	75	6 (if ZW25 de-escalation from cohort 1C, palbociclib de-escalation from cohort 1E, or both ZW25 and palbociclib de-escalation from cohort 1B recommended)
2	2	RD ^a	RD ^a	Approximately 50

IV = intravenous; PO = orally (per oral); RD = recommended dose; Q2W = every 2 weeks.

^a RD established in Part 1

^b Part 1 sample sizes are based on the number of DLT evaluable subjects. Part 2 sample size is based on the approximate number of subjects planned for enrollment.

Notes: Cohorts 1A through 1F are not necessarily sequential. ZW25 is given IV Q2W. Step-down dose level to 15 mg/kg Q2W or another dose level (not lower than 15 mg/kg) of ZW25 may be evaluated if recommended by the SMC and approved by the sponsor. palbociclib is taken PO QD on Days 1 through 21 of each 28-day cycle. There are no step-down doses for toxicity for fulvestrant.

A subject will be considered DLT evaluable if he or she has received $\geq 75\%$ of the planned total dose of each component of study treatment (ZW25, palbociclib, and fulvestrant) over the first 28 days of treatment, and was followed for the full DLT evaluation period, unless the reason for not receiving required doses or not being followed was the occurrence of a DLT. Subjects who are considered not evaluable for DLT may be replaced. The probabilities of observing DLTs in a cohort of 6 subjects for Part 1 are summarized in [Table 10](#).

Table 10: Probabilities of observing DLTs in Part 1

N = 6 Subjects	True DLT Incidence				
	5%	10%	20%	30%	40%
Probability of 0 DLTs	0.74	0.53	0.26	0.12	0.05
Probability of ≤ 1 DLTs	0.97	0.89	0.66	0.42	0.23
Probability of De-escalation (≥ 2 DLTs)	0.03	0.11	0.34	0.58	0.77

DLT = dose-limiting toxicity

In Part 2 of the study, approximately 50 subjects are expected to be enrolled. Assuming the observed PFS6 rate is between 40% and 70%, the corresponding 95% binomial exact confidence intervals (CI) are summarized in [Table 11](#) below.

Table 11: PFS6 Rate and Corresponding 95% Confidence Intervals

PFS6 Rate	Binomial exact 95% CI (N=50)
40%	(26%, 55%)
50%	(36%, 64%)
60%	(45%, 74%)
70%	(55%, 82%)

Therefore, a total of up to approximately 86 subjects may be enrolled across the entire study.

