A subject will be considered DLT-evaluable if he/she has received $\geq 75\%$ of the planned total dose of each component of study treatment (ZW25, palbociclib, and fulvestrant) over the first 28 days of treatment, and was followed for the full DLT evaluation period, unless the reason for not receiving required doses or not being followed was the occurrence of a DLT. If the reason for not receiving required doses is a DLT, a subject will still be considered evaluable. To account for potential discontinuations prior to being evaluable for DLT (for example, progressive disease [PD] or subject preference), enrollment of replacement subjects will be allowed to permit assessment of DLTs and recommended dose level for Part 2.

Dose-limiting toxicities, defined using the (NCI CTCAE) version 5.0, are events that 1) occur following administration of ZW25, palbociclib, and fulvestrant, or any combination of ZW25 and 1 or more of these drugs; and 2) meet the criteria described below. Events for which there is an alternative clinical explanation (e.g., clearly related to an intercurrent illness, disease progression, or extraneous causes) will not be considered DLTs. The relationship of AEs to each component of study treatment will be determined by the investigator; however, the Sponsor and/or the SMC may query the relationship assessments and/or determine that the event was related to additional components of the regimen.

DLT Criteria Non-Hematologic

Any non-hematologic AE \geq Grade 3 in severity that is not clearly and incontrovertibly due to disease progression or extraneous causes (e.g., accidental injury or similar event) is considered a DLT, with the following exceptions:

- Grade 3 fatigue lasting ≤ 3 days
- Grade 3 diarrhea, nausea, or vomiting that resolves to \leq Grade 1 or baseline within 3 days with adequate supportive care
- Grade 3 rash without maximal use of corticosteroids or anti-infectives
- Infusion reaction \leq Grade 3 (for management of infusion reactions, see [Section 5.2.3.2](#))

Grade 2 or greater events of pneumonitis and/or interstitial lung disease, including pulmonary fibrosis not clearly and incontrovertibly related to disease progression or extraneous causes is considered a DLT.

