9.2 Analysis Sets

For the purposes of analysis, the subject analysis sets are defined in [Table 12](#).

Table 12: Subject Analysis Sets

Analysis Set	Description
All Enrolled Subjects	All participants who sign the informed consent form and receive approval from the sponsor to be enrolled and treated.
Safety Analysis Set	All participants enrolled in the study who receive any amount of ZW25, palbociclib, and/or fulvestrant.
DLT Evaluable Set	All subjects who receive $\geq 75\%$ of the planned total dose of each component of study treatment (ZW25, palbociclib, and fulvestrant) over the first 28 days of treatment, and are followed for the full DLT evaluation period, unless the reason for not receiving required doses or not being followed is the occurrence of DLT.
mITT Set	All subjects in the safety analysis set who had at least one identifiable (target and/or non-target) lesion at baseline and at least one post-baseline disease assessment or discontinued all study treatment and are no longer being followed for efficacy.
Measurable Disease	All subjects in the safety analysis set who had at least one measurable target lesion at baseline and at least one post-baseline disease assessment or discontinued the study due to death, clinical or radiologic progressive disease, or an AE.
Pharmacokinetics	All subjects in the safety analysis set who have sufficient post-dose samples collected to allow estimation of the PK. Subjects who have protocol deviations that could affect the PK evaluation, will be noted and may be excluded from the PK analysis set depending on the type of the deviation.

AE= adverse event; DLT = dose-limiting toxicity; mITT = modified intent to treat; PK= pharmacokinetics

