9.3.9.2 Dose-limiting Toxicities (DLTs)

The frequency of DLTs (as defined in [Section 3.1.2](#)) and the corresponding exact binomial 95% CI will be calculated for each dose cohort for Part 1 of the study only. This will be computed for the DLT Evaluable Set.

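### A subject with a DLT falls outside the DLT Evaluable Set, and may be replaced, when the missed dose or lost follow-up had another cause

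*Combined protocol and SAP*

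**What the plan says.** Section 9.1 requires at least 75% "of the planned total dose of each component of study treatment (ZW25, palbociclib, and fulvestrant) over the first 28 days of treatment", plus follow-up for the whole DLT period. The only way round either requirement is the clause "unless the reason for not receiving required doses or not being followed was the occurrence of a DLT". Table 12 in section 9.2 repeats it for the DLT Evaluable Set: "unless the reason for not receiving required doses or not being followed is the occurrence of DLT". The synopsis uses the same rule.

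Section 3.1.2 and the synopsis sample-size text add one sentence, here in the 3.1.2 wording: "If the reason for not receiving required doses is a DLT, a subject will still be considered evaluable". It restates the causal condition and does not widen it. Nowhere does the plan say that a subject with a DLT is evaluable whatever the exposure or follow-up.

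On replacement, section 9.1 says: "Subjects who are considered not evaluable for DLT may be replaced". Section 3.1.2 gives the purpose, with examples: "To account for potential discontinuations prior to being evaluable for DLT (for example, progressive disease [PD] or subject preference".

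Two results rest on this set. Section 3.1.2 calls a dose level not tolerated when at least 2 of 6 DLT evaluable subjects have a DLT. Section 9.3.9.2 says of the DLT frequency and its exact interval: "This will be computed for the DLT Evaluable Set". DLT frequency is listed first among the Part 1 primary endpoints in section 2.1.

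The next sentence of 3.1.2, on when the SMC may recommend a step-down, refers to DLTs in at least 2 subjects and omits the word evaluable.

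**The concern.** The exposure and follow-up tests are there so that a subject who was barely treated or observed is not counted as having tolerated the dose. That reasoning applies to subjects without a DLT. Once a DLT has been seen, low exposure does not make it uninformative; if anything, a toxicity at less than full dose is stronger evidence against the dose.

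The clause as written also removes subjects who had the event, if the shortfall or exit arose elsewhere. Cases that meet the wording are:

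- a Day 15 ZW25 or fulvestrant dose missed for logistics, with a DLT before or after it;
- a palbociclib hold for something that is not a DLT, leaving fewer than 16 of 21 doses, followed by a DLT;
- consent withdrawn inside the window, for a reason other than the DLT, after a DLT that did not itself reduce dosing.

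At stake are the formal tolerability count for the dose taken to about 50 Part 2 subjects, and the DLT rate reported for Part 1.

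**Working it through.** **1. The plan's own figures.** Table 10 is Binomial(6, p). At p = 0.30: P(0) = 0.7^6 = 0.118; P(≤1) = 0.7^6 + 6(0.3)(0.7^5) = 0.420; P(≥2) = 0.580. All 15 cells reproduce to two decimals; P(≥2) is 0.033, 0.114, 0.345, 0.580 and 0.767 at 5, 10, 20, 30 and 40%.

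**2. How easily the 75% test is missed.** ZW25 has two doses in the window (section 5.2.2, Days 1 and 15), as does fulvestrant (section 5.3.2). One miss gives 1/2 = 50%. Section 5.2.3 requires a Day 15 ZW25 dose to be skipped if it is more than 6 days late. Palbociclib has 21 daily doses: 16/21 = 76.2% passes and 15/21 = 71.4% fails.

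**3. One cohort.** Suppose 2 of 6 treated subjects have a DLT, and one of the two missed the Day 15 ZW25 dose for an unrelated reason.

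| Handling | DLTs / evaluable | Exact 95% CI |
|---|---|---|
| Excluded, replaced by a DLT-free subject | 1/6 = 16.7% | 0.4% to 64.1% |
| Kept, no replacement | 2/6 = 33.3% | 4.3% to 77.7% |
| Kept, seventh DLT-free subject added | 2/7 = 28.6% | 3.7% to 71.0% |

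The first row is within the limit; the second is not tolerated.

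**4. Operating characteristics.** Let p be the true DLT rate, w the share of DLT subjects and v the share of DLT-free subjects made non-evaluable for a reason other than a DLT. The documents give neither w nor v, so the values below are assumptions.

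Current rule: evaluable-set rate = p(1−w) / [p(1−w) + (1−p)(1−v)].

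Proposed rule: rate = p / [p + (1−p)(1−v)], which does not depend on w.

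Pass means 0 or 1 DLT in 6. At p = 0.30 and v = 0.20:

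| w | Current rate | Current P(pass) | Proposed rate | Proposed P(pass) |
|---|---|---|---|---|
| 0.40 | 0.18/0.74 = 24.3% | 0.55 | 0.30/0.86 = 34.9% | 0.32 |
| 0.20 | 0.24/0.80 = 30.0% | 0.42 | 34.9% | 0.32 |
| 0.10 | 0.27/0.83 = 32.5% | 0.37 | 34.9% | 0.32 |

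The current rule understates the DLT rate if w > v, is unbiased if w = v, and overstates it if w < v.

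**5. Price of the proposed rule when loss is unrelated to DLT** (w = v = 0.20). At p = 0.30, P(≥2 of 6) rises from 0.58 to 0.68. At p = 0.10 the rate becomes 0.10/0.82 = 12.2% and P(≥2 of 6) rises from 0.11 to 0.16.

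**The case against.** The best counter-argument is that the rule is not mechanical. Replacement is optional. The SMC may recommend a step-down at any time on the overall safety picture, may enrol more than 6 subjects at a level, and decides on the move to Part 2. One of the two triggers in 3.1.2 does not mention evaluability. The event stays in the by-cohort adverse event summaries on the Safety Analysis Set (section 9.3.9), which also serve Part 1 primary endpoints. All of this stands, so the pass probabilities describe the formal count only. It does not repair that count or the DLT frequency table.

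Three stronger readings are tempting, and the documents do not support them.

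- *That a subject who has a DLT and later stops for progression is lost.* A reader might infer this from the replacement examples in 3.1.2 ("for example, progressive disease [PD] or subject preference"). Progression ends treatment but is not a reason for study withdrawal (section 4.4.2), and adverse events are collected to 30 days after the last dose (section 7.7.1.3). A subject dosed to about Day 20 would have both Day 15 injections and some 19 of 21 palbociclib doses. Progression could remove a subject only by leaving dosing short. If the DLT itself caused the shortfall, 3.1.2 keeps the subject.
- *That non-DLT palbociclib holds will be common in Cycle 1.* The 66% with Grade 3 or higher neutrophil decrease in section 1.8.3 comes from a trial with a median treatment duration of 10.8 months (section 1.8); the 15-day median is for first neutropenia of any grade; and hold rules are left to the prescribing information (section 5.3.3). None of these gives a Cycle 1 frequency.
- *That the bias must favour the dose.* Clustering of toxicities would make w exceed v. But DLTs that themselves cause the hold leave the subject evaluable, so w could be below v.

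**Conclusion.** The point holds on the text. Followed literally, the definition in the synopsis, 3.1.2, 9.1 and Table 12 can exclude an observed, protocol-defined DLT from the formal tolerability count and from the reported DLT frequency. It does not remove the event from the safety data or from the SMC's view.

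The average effect cannot be sized from the documents, and its direction depends on assumed loss rates: at a true rate of 30%, a pass probability of 0.55, 0.42 or 0.37 in the three scenarios, against 0.42 in Table 10. What does not depend on those assumptions is that, with 6 subjects and a limit of 2, one excluded DLT can reverse a cohort's result. Section 9.3 leaves detail to an SAP finalised before database lock; nothing in the document at hand settles the point.

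**What to change.** In the synopsis, 3.1.2, 9.1 and Table 12, define a DLT evaluable subject as either (i) any treated subject with a DLT in the 28-day period, whatever the dose received or length of follow-up, or (ii) a subject without a DLT who received at least 75% of each component and was followed for the full period. Allow replacement only of DLT-free subjects who fail (ii).

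Reconcile the two adjacent sentences in 3.1.2, one counting DLT evaluable subjects and the other simply subjects, so that the tolerability rule and the step-down trigger have a stated common or deliberately different denominator.

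Add a note under Table 10, and under the matching Table 2 in the synopsis, that the probabilities assume no subject is lost for other reasons.

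No new data are needed. The cost is some conservatism when loss is unrelated to toxicity: at 20% loss, a true 30% is estimated as about 35%, and false de-escalation at a true 10% rises from 0.11 to 0.16. If dose selection is already complete, the definition can still be set in the SAP for reporting, with any DLT in a non-evaluable subject listed by cohort.
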